7.6.7 Reporting of tumor response

All patients included in the study must be assessed for response to treatment, even if there is a major protocol treatment deviation or if they are ineligible, or not followed/re-evaluated. Each patient will be assigned one of the following categories: CR/iCR, PR/iPR, SD/iSD, PD/iCPD, early death from malignant disease, early death from toxicity, or early death from other cause or unknown (not assessable, insufficient data).

Early death is defined as any death occurring <30 days after randomization. Clinical Investigator will decide if the cause of death is malignant disease, toxicity, or other.

Patients for whom response is not confirmed will be classified as *Unknown*, unless they meet the criteria for SD/iSD (or the criteria for PR/iPR in case of an unconfirmed CR/iCR). Patients' response will also be classified as *Unknown* if insufficient data were collected to allow evaluation per these criteria.

7.6.8 Response duration

This will be measured from the time of randomization, or until the first date that recurrent or progressive disease is objectively documented. Patients who have not had PD/iCPD at the time of final analysis will be censored at the date last known to be alive and progression-free.

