2 STUDY OBJECTIVES AND END POINTS

Hypothesis: Most patients with metastatic CRC harbor tumor that can be transformed into an immunogenic disease by oxaliplatin, and may thereby benefit from the addition of immune-modulating therapy to improve outcome of the current oxaliplatin-based standard-of-care.

	Objectives	End points
Primary	
To determine PFS, in terms of failure of treatment strategy, on sequential treatment with the Nordic FLOX regimen and nivolumab² compared with the standard-of-care Nordic FLOX regimen in previously untreated MSS metastatic CRC.
 
² Nivolumab is an ICB agent.
	
 – PFS: radiologic assessment every 8 weeks (following 4 cycles of FLOX or the alternative 2 cycles each of FLOX and nivolumab), according to the Response Evaluation Criteria in Solid Tumors (RECIST) and the RECIST consensus guideline for assessment of response to immune-modulating therapies, iRECIST (c.f., Appendices 1 and 2).
Secondary	
To determine safety and tolerability of sequential treatment with the Nordic FLOX regimen and nivolumab compared with the standard-of-care Nordic FLOX regimen.
 
To determine objective response rate (ORR), duration of response (DOR), secondary surgical curative resection rate (SSCRR), and OS.
	
 – Safety: incidence of adverse events (AE), as reported according to Common Terminology Criteria for Adverse Events (CTCAE) version 4.0 (c.f., Appendix 3) recorded on onboing basis, and summarized every 4 weeks on active study therapy and every 8 weeks in planned breaks from active study therapy. – Tolerability: AE grading, as assessed by CTCAE v4.0 recorded on onboing basis, and summarized every 4 weeks on active study therapy and every 8 weeks in planned breaks from active study therapy. – ORR: the percentage of patients with a confirmed complete or partial response. – DOR: the time from the first documentation of a complete or partial response to disease progression. – SSCRR: the percentage of patients with a confirmed resection of metastatic disease with microscopically free margin (R0). – OS: the time from randomization to death of any cause.

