7.6 Tumor imaging and assessment of disease procedures

7.6.1 Evaluation of efficacy

The imaging assessments will be performed by CT, typically a thoracic/abdominal/pelvic CT scan. Tumor treatment response will be assessed according to RECIST v1.1 as the primary method and iRECIST as the secondary method. After baseline tumor assessments, evaluation of tumor response will be performed every 8 weeks (± 7 days). Additional MR scans or other radiologic evaluations will be performed if indicated.

All radiologic examinations will be transmitted to Study Radiologist at Akershus University Hospital within 1 working day after the scan is performed. A radiologist at the actual study center will evaluate the images for incidental findings that may have a therapeutic consequence (e.g., pulmonary embolism, immune therapy-related findings that require emergency actions).

Study Radiologist will be blinded to patient treatment, but will be informed about treatment breaks in the go-and-stop schedule. Study Radiologist will primarily assess tumor measures according to RECIST v1.1. If disease progression is concluded by means of RECIST v1.1, Study Radiologist will also assess tumor measures according to iRECIST. The radiology report will detail the criteria used for Clinical Investigator to make a decision about further study treatment (*c.f.*, [Paragraph 5.7.2.4](#)).

PFS will be calculated from the day of randomization to first recorded disease progression according to RECIST v1.1 or iRECIST when applicable, or death. Patients who have not had disease progression at the time of final analysis will be censored at the date last known to be alive and progression-free.

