7.6.5 Frequency of tumor re-evaluation

Frequency of tumor re-evaluation will be every 8 weeks in both arms and during planned study treatment breaks. In the case of suspected clinical progression or iUPD according to iRECIST, the next evaluation may be preponed to after 4 weeks.

Evaluation will be with routine CT of the thoracic/abdominal/pelvic cavities, preferably with contrast in the case of adequate renal function.

If brain or bone metastasis is suspected, supplemental MR evaluations may be undertaken. However, bone scans only need to be repeated when CR is identified in target disease or when progression in bone is suspected.

All target and non-target sites are assessed at each evaluation.

After discontinuation of protocol treatment, patients who have not progressed will still be re-evaluated every 8 weeks until end-of-study, as per protocol.

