7.6.9 Stable disease duration

This will be measured from the time of randomization until the criteria for progression are met. Patients who have not had PD/iCPD at the time of final analysis will be censored at the date last known to be alive and progression-free.

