### 5. Analysis

#### 5.1. End point definitions

*Primary end point:* PFS; radiologic assessment every 8 weeks, according to the Response Evaluation Criteria in Solid Tumors (RECIST) and the RECIST consensus guideline for assessment of response to immune-modulating therapies, iRECIST.

*Secondary end points:*

Safety: incidence of adverse events (AE), as reported according to Common Terminology Criteria for Adverse Events (CTCAE) version 4.0 recorded on ongoing basis.

Tolerability: AE grading, as assessed by CTCAE v4.0 recorded on ongoing basis.

ORR: the percentage of patients with a confirmed complete response (CR) or partial response (PR).

DOR: the time from the first documentation of a CR or PR to disease progression.

SSCRR: the percentage of patients with a confirmed resection of metastatic disease with microscopically free margin (R0).

OS: the time from randomization to death of any cause.

QoL: assessment undertaken at study enrolment, completion of the active therapy of the first treatment sequence (after 16 weeks), and disease progression, using the consensus modules EORTC QLQ-C30, EORTC QLQ-CIPN20, and EQ-5D-5L.

*Tertiary end point:* Cost estimate; evaluation of the healthcare costs (relating to the sequencing procedures and administered medication) and health effects (quality-adjusted life years), expressed as incremental cost-effectiveness ratio, of the sequential therapy relative to the control group as comparator.

*Exploratory end points:* Various analyses will be undertaken for exploratory end points listed in 1.2.

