Tolerability. Summaries by trial arm will be produced to show the proportion of participants experiencing each grade of CTCAE toxicities overall and during each treatment cycle. For more detailed summaries, this information will also be broken down into the different types of toxicities.

QoL. This will be summarized for each treatment arm at study enrolment, completion of the active therapy of the first treatment sequence (after 16 weeks), and disease progression, using the consensus modules EORTC QLQ-C30, EORTC QLQ-CIPN20, and EQ-5D-5L. The data will be illustrated graphically and presented as mean scores with 95% CI at separate time points. The differences in QoL between two treatment arms throughout the study period will be assessed by estimating a linear mixed model with fixed effects for time and treatment arm and the interaction between these two. Random effects for patients will be included. A significant interaction will quantify differences between the groups and serve as an omnibus test.

Safety and tolerability in the treatment arms will be compared by  $\chi^2$  or Fisher's exact test, as appropriate.

ORR is defined as the percentage of patients with a confirmed CR or PR. The proportion of participants achieving at least PR will be summarized with corresponding 95% CI for each treatment arm. The difference between the trial arms in the proportion of participants achieving at least PR will also be presented with corresponding 95% CI. The difference between participants achieving at least PR and remaining participants will be assessed using logistic regression adjusting for treatment group and stratification factors. Odds ratios with corresponding 95% CI and p-values will be presented for all variables incorporated in the model.

SSCRR is defined as the percentage of patients with a confirmed resection of metastatic disease with microscopically free margin (R0). Corresponding analyses as those to be performed for ORR will be applied for SSCRR.

DOR is defined as the time from the first documentation of CR/iCR or PR/iPR to disease progression. DOR Kaplan-Meier curves will be drawn and compared by log-rank test. The median DOR with corresponding 95% CI will be presented by treatment group. Stratified analyses will be performed as well. The Cox proportional hazards model, adjusting for the stratification factors, will also be used to compare DOR

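### Protocol 7.6.8 starts response duration at randomization, against the DOR definition used everywhere else; if applied, it would lengthen each responder's DOR by that patient's time to first documented response

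*Protocol*

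**What the plan says.** Protocol 7.6.8 (Response duration): "This will be measured from the time of randomization, or until the first date that recurrent or progressive disease is objectively documented". Its second sentence censors patients without PD/iCPD at the final analysis at the date they were last known to be alive and progression-free.

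Protocol 7.6.9 (Stable disease duration) has the same origin and the same censoring sentence: "This will be measured from the time of randomization until the criteria for progression are met".

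The end point itself is defined differently, and consistently, in four places:

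- Protocol section 2, end-point table: "DOR: the time from the first documentation of a complete or partial response to disease progression".
- Protocol 10.4.5: from first documentation of CR/iCR or PR/iPR to progression.
- SAP 5.1: "DOR: the time from the first documentation of a CR or PR to disease progression".
- SAP 5.2: "DOR is defined as the time from the first documentation of CR/iCR or PR/iPR to disease progression".

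Protocol 10.4.5 and SAP 5.2 plan Kaplan-Meier curves, a median with 95% CI, a log-rank test and a Cox model for DOR.

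**The concern.** The documents give two start dates for one quantity, and no text says which takes precedence. The sentence in 7.6.8 cannot be followed literally, since it names a start and then offers an end as an alternative to it. Because its origin is that of 7.6.9, it reads as if the stable-disease rule had been carried over.

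The discrepancy is not purely cosmetic, because a Kaplan-Meier analysis of DOR needs a censoring rule. The four DOR definitions give none, and the rule in Protocol 10.4.1 and SAP 5.2 is written for PFS. Section 7.6.8 is the only text that states a censoring rule for response duration. An analyst who goes there for it finds the wrong origin beside it.

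What is at stake is the reported length of response. Under 7.6.8, time before any response counts as time in response.

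**Working it through.** The documents state no DOR figure, so there is none to reproduce.

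**Size of the offset for one responder.** Let R be randomization, F the first documented response and P the progression that ends the response.

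- Duration under 7.6.8 = P − R.
- Duration under the four DOR definitions = P − F.
- Difference = (P − R) − (P − F) = F − R, the patient's own time to first documented response.

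**Possible values of F − R.** Protocol 7.6.1 sets scans every 8 weeks, ± 7 days, and Protocol 7.6.5 adds: "Frequency of tumor re-evaluation will be every 8 weeks in both arms and during planned study treatment breaks".

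| First response seen at | Offset (window), weeks |
|---|---|
| Scan 1 | 8 (7–9) |
| Scan 2 | 16 (15–17) |
| Scan 3 | 24 (23–25) |
| Scan 4 | 32 (31–33) |

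Any gap between randomization and first dose is added. The documents give no figure for it. If the flow chart's screening window of up to 15 days is taken as its limit (an assumption), it adds up to about 2 weeks. The lower end is not strict either: after suspected clinical progression or iUPD, "the next evaluation may be preponed to after 4 weeks".

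**Effect on single patients.** Protocol 5.5 describes an average patient who first progresses at week 24 in both arms (16 weeks of therapy plus 8 weeks of break). Failure of treatment strategy follows at week 40 (control) or week 80 (experimental). The table uses each of these as a possible end date. The 40- and 80-week rows apply only if DOR is taken to end at strategy failure.

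| End date, weeks | First response, week | DOR from response | Under 7.6.8 | Ratio |
|---|---|---|---|---|
| 24 (both arms) | 8 | 16 | 24 | 1.50 |
| 40 (control) | 8 | 32 | 40 | 1.25 |
| 40 (control) | 16 | 24 | 40 | 1.67 |
| 80 (experimental) | 8 | 72 | 80 | 1.11 |
| 80 (experimental) | 16 | 64 | 80 | 1.25 |

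**Effect on the median, under stated assumptions.** Assume that 70% of responders first respond at week 8 and 30% at week 16, that every response is held for 8 weeks, and that time thereafter is exponential with the plan's medians of 39 and 78 weeks.

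- From first response, the medians are 8 + 39 = 47 and 8 + 78 = 86 weeks.
- From randomization, the median t solves 0.7·exp(−λ(t − 16)) + 0.3·exp(−λ(t − 24)) = 0.5 with λ = ln 2/39 or ln 2/78. This gives t = 57.5 and 96.5 weeks.
- The increase is about 10.5 weeks in each arm: 57.5/47 = 1.22 and 96.5/86 = 1.12.

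**Effect on the planned comparison.** Log-rank and Cox depend only on the order of the times, so an equal shift for every responder changes neither. In the scenario above, simulated with 40,000 patients per arm and no censoring, the Cox hazard ratio is 0.501 from either origin. It would move if time to response differed materially between patients or arms.

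**The case against.** The strongest reply is that the analysis is already defined. Four definitions agree, two of them in the sections that govern the analysis, and the SAP does not repeat the 7.6.8 sentence. That sentence is visibly garbled, so nobody is likely to run it. This largely stands: analysis from randomization is unlikely, and the point is minor. It does not make 7.6.8 right, and 7.6.8 still holds the only censoring rule for response duration.

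A reader might also infer more than the documents support:

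- *That every DOR gains 8 to 16 weeks.* Nothing confines first response to the first two scans. Protocol 7.6.3 scores best response from start to end of treatment, and 7.6.4 foresees delayed responses. The 2–4 months to response cited in 5.5 is a median from other tumor types.
- *That the between-arm comparison is distorted.* With first response at week 8, the 40- and 80-week figures give an arm ratio of 72/32 = 2.25 from response and 80/40 = 2.0 from randomization. Those are strategy-failure dates, however. With first progression at week 24 in both arms, the ratio is 1.0 either way. The plan also analyses no ratio of durations. A later response in the experimental arm could shift the log-rank and Cox results, but no document gives a size for that.
- *That 7.6.8 turns DOR into PFS among responders.* It is close, but PFS counts death and 7.6.8 ends only at recurrence or progression.
- *That the CRF or radiology derivations follow 7.6.8.* No text says so. Protocol 7.6.2.2 puts lesion measurements on the CRF, not DOR.

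**Conclusion.** Wrong as written, minor. Protocol 7.6.8 contradicts the DOR definition in Protocol section 2, Protocol 10.4.5 and SAP 5.1 and 5.2. If applied, it would lengthen each responder's DOR by the time from randomization to first documented response, with no upper limit set by the documents. The median DOR would rise too, by about 10.5 weeks in each arm in the illustrated scenario. That figure rests on the assumed 70/30 split, the 8-week hold and the same response timing in both arms. The contradiction itself rests on none of these.

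The between-arm test and hazard ratio would be materially affected only if time to response varies enough between patients or arms. The primary PFS analysis and the sample size do not depend on 7.6.8.

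**What to change.** Replace the first sentence of Protocol 7.6.8 with: *Response duration is measured from the date of the first scan documenting a subsequently confirmed CR/iCR or PR/iPR until the date of progression as used for the DOR end point.* Naming iCR and iPR keeps it in line with Protocol 10.4.5 and SAP 5.2.

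Keep the existing censoring sentence of 7.6.8. Keep randomization as the origin for stable-disease duration in 7.6.9 only.

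The cost is one protocol sentence. It needs no new data and changes neither the SAP definitions, the primary analysis nor the sample size. DOR values will be shorter than 7.6.8 would have given.

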7.6.9 Stable disease duration

This will be measured from the time of randomization until the criteria for progression are met. Patients who have not had PD/iCPD at the time of final analysis will be censored at the date last known to be alive and progression-free.

7.7 Other study procedures

7.7.1 Screening period

Approximately 7–14 days prior to subject allocation, potential subjects will be evaluated to determine that they fulfill the entry requirements. Results of a test performed prior to the subject signing consent as part of routine clinical management are acceptable in lieu of a screening test if performed within the specified time frame. Screening procedures can not be completed earlier than 14 days prior to the first dose of trial treatment except for WOCBP, for whom a serum pregnancy test will be performed within 24 hours prior to the first dose of trial treatment. A urine test may be considered if serum test is not appropriate.

Subjects may be rescreened after initially failing to meet the inclusion/exclusion criteria. Results from assessments performed during the initial screening period are acceptable in lieu of a repeat screening test if performed within the specified time frame and the inclusion/exclusion criteria are met.

7.7.2 Treatment period

Visit requirements are outlined in [Chapter 6](#) – Study Flow Chart. Specific procedure-related details are provided in [Chapter 7](#) – Study Procedures.

7.7.3 Post-treatment visits

7.7.3.1 Safety follow-up visit

The mandatory safety follow-up visit will be conducted approximately 30 days after the last dose of trial treatment or before the initiation of a new anti-cancer treatment, whichever comes first. All AE that occur prior to the safety follow-up visit should be recorded. Subjects with an AE of CTCAE grade >1 will be followed until the resolution of the AE to grade 0–1 or stabilization, or until the beginning of a new anti-neoplastic therapy, whichever occurs first. SAE that occurs within

the full duration of the study (*c.f.*, [Paragraph 7.8](#)) or before initiation of a new anti-cancer treatment will also be followed and recorded.

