The optimum duration of immune-modulating therapy is currently unknown. However, because such therapy engages the immune system to control the tumor, continuous treatment, as is required with other types of biologically targeting agents or systemic cytotoxic therapies, may not be necessary.

Accumulating evidence from different clinical trials in different tumor types with nivolumab or nivolumab combined with the ICB drug ipilimumab indicates that most of the responses are generally occurring early, with a median time to response of 2–4 months [Brahmer *et al.*, 2015; Borghaei *et al.*, 2015; Hellmann *et al.*, 2016; Larkin *et al.*, 2015; Motzer *et al.*, 2015]. A recent analysis in a melanoma study suggests the majority of patients who discontinue nivolumab and/or ipilimumab for toxicity maintain disease control in the absence of further treatment (Schadendorf D *et al.*, reported at the 2016 Annual Meeting of the European Association of Dermato-Oncology in Vienna, Austria). Furthermore, a limited duration of ipilimumab including only 4 induction doses resulted in long-term survival in patients with metastatic melanoma, with a sustained plateau in survival starting at around year 3 [Schadendorf *et al.*, 2015].

For these reasons, in the present study, a total of 24 months of active sequential FLOX and nivolumab therapy will be administered, given the absence of disease progression (while the subject is on active therapy) or unacceptable toxicity at an earlier treatment time. After 24 months, FLOX alone may be administered as per the study dosing schedule in the control arm. Experimental arm subjects who complete a total of 24 months of active sequential FLOX and nivolumab therapy and have subsequent disease progression (on or off FLOX alone) may, at the discretion of Clinical Investigator, reinstitute sequential FLOX and nivolumab at the same dose and schedule given previously on study, and continue such treatment for up to 1 additional year. Continuation of treatment with FLOX beyond a total of 24 months of active sequential FLOX and nivolumab therapy (*i.e.*, 12 months of active FLOX) is contingent on continued tolerance for FLOX.

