All concomitant medications received within 28 days before the first dose of study treatment and 30 days after the last dose of study treatment will be recorded. Concomitant medications administered later than 30 days after the last dose of study treatment should be recorded for SAE.

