Laboratory analyses ¹³	X	X ¹⁴	X ¹⁴	X ¹⁴	X ¹⁴	
Urine analysis ¹⁵	X	X ¹⁴	X ¹⁴	X ¹⁴	X ¹⁴	
Treatment administration						
FLOX						
Nivolumab						
Evaluation procedure(s)						
CT ¹⁷	X	X				
Correlative study procedures						
Whole blood sampling						
Plasma and serum sampling	X	X				
PBMC sampling ¹⁹	X	X				
Functional MR liver acquisition ^{19,20}						
Liver/peritoneal biopsy sampling ²¹						

- 1 Repeat after break period with disease progression, continue until progressive disease on ongoing therapy.
- 2 Until disease progression.
- 3 Analysis on primary or metastatic tumor.
- 4 Only at visit 2.
- 5 By completion of the active therapy of the first treatment sequence (after 16 weeks), *i.e.*, at first visit in first treatment break.
- 6 Until all study drug-related AE are resolved, have returned to baseline, or are deemed irreversible; reported for at least 100 days after last dose administration of IMP.
- 7 To be undertaken if clinically indicated from V1 onward, but mandatory at the 30 days safety follow-up visit.
- 8 May be omitted if full physical examination has been undertaken 14 days or less prior to the first dose of trial treatment.
- 9 For WOCBP.
- 10 Within 24 hours prior to the start of study drug.
- 11 Every 4 weeks.
- 12 Every 4 weeks; in the control arm, for 30 days after the last dose of study drug; in the experimental arm, for 160 days after the last dose of study drug.
- 13 Laboratory tests: Hb, HCT, WBC (including differential counting), platelets, liver factors (ALT, AST, ALP, LDH, GGT, total bilirubin, total albumin, INR), creatinine or urea, Na, K, Ca, Mg, phosphate, glucose, TSH, free T4, CEA, Ca19.9, Ca125.
- 14 Until all study drug-related abnormalities are resolved, have returned to baseline, or are deemed irreversible.
- 15 Dipstick.
- 16 FLOX in control treatment arm, nivolumab in experimental treatment arm.
- 17 In addition to computed tomography (CT) scan, MR scans or other radiologic evaluations will be performed if indicated.
- 18 Baseline CT scan must be taken within 28 days prior to the start of study drug.
- 19 Participation is optional for study centers.
- 20 Patient must not present contraindication to the procedure. Procedure must be done before a metastatic lesion in the liver/peritoneum is sampled.
- 21 Baseline sampling is mandatory; follow-up sampling is optional.

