7.3.5 Subsequent anti-cancer therapy status

Clinical Investigator or a qualified designee will review all new anti-neoplastic therapy initiated after the last dose of trial treatment. If a subject initiates a new anti-cancer therapy within 30 days after the last dose of trial treatment, the 30 day safety follow-up visit must occur before the first dose of the new therapy. Once new anti-cancer therapy has been initiated the subject will move into survival follow-up.

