7.7.4 Withdrawal or discontinuation

When a subject discontinues or withdraws prior to trial completion, all applicable activities scheduled for the final trial visit will be performed at the time of discontinuation. Any AE which are present at the time of discontinuation will be followed in accordance with the safety requirements outlined in [Chapter 8](#).

Subjects may withdraw consent at any time for any reason or be dropped from the trial at the discretion of Clinical Investigator should any untoward effect occur. In addition, a subject may be withdrawn by Clinical Investigator or Sponsor if enrolment into the trial is inappropriate, the trial plan is violated, or for administrative and/or other safety reasons. A subject must be discontinued from the trial for any of the following reasons:

- AE/SAE as specifically described.
- The subject withdraws consent.
- Confirmed disease progression; *c.f.*, [Paragraph 7.6](#).
- Any clinical AE, laboratory abnormality, or intercurrent illness which, in the opinion of Clinical Investigator, indicates that continued participation in the study is not in the best interest of the subject.
- Intercurrent illness that prevents further administration of treatment.
- Clinical Investigator's decision to withdraw the subject.
- The subject has a confirmed positive pregnancy test.
- Non-compliance with trial treatment or procedure requirements.
- The subject is lost to follow-up.
- Administrative reasons.

After the end of treatment, each subject will be followed for 30 days for AE monitoring. Subjects who discontinue for reasons other than PD/iCPD will have post-treatment follow-up for disease status until disease progression, starting a non-study cancer treatment, withdrawing consent, or becoming lost to follow-up. After documented disease progression, information on survival will be obtained until death, withdrawal of consent, or the end of the study, whichever occurs first.

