8.2 SAE (serious adverse events) collection and reporting

For nivolumab, the IB represents the reference safety information to determine expectedness of SAE for expedited reporting. For the FLOX regimen, the SmPC of each of the drug components represents the reference safety information. Following the subject's written consent to participate in the study, all SAE (in both study arms), whether related or not related to study drug, must be collected, including those thought to be associated with protocol-specified procedures. All SAE must be collected that occur during the screening period and within 100 days of the last dose of nivolumab. If applicable, SAE must be collected that relate to any later protocol-specified procedure.

Clinical Investigator must report any SAE that occurs after these time periods and that is believed to be related to any IMP or protocol-specified procedure, pertaining to the full duration of the study (c.f., Paragraph 7.8), which is in accordance with European Commission guidelines.

An SAE report must be completed for any event where doubt exists regarding its seriousness.

If Clinical Investigator believes that an SAE is not related to study drug, but is potentially related to the conditions of the study (such as withdrawal of previous therapy or a complication of a study procedure), the relationship must be specified in the narrative section of the SAE report form.

SAE, whether related or not related to study drug, and pregnancies, must be reported to Sponsor (or designee) within 24 hours of awareness of the event. SAE will be recorded on the Suspect Adverse Reaction Report form by the Council for International Organizations of Medical Sciences (CIOMS), c.f. Appendix 10. Pregnancies will be recorded on a Pregnancy Surveillance Form.

If only limited information is initially available, follow-up reports are required. All SAE must be followed to resolution or stabilization.

If an ongoing SAE changes in its intensity or relationship to study drug or if new information becomes available, the SAE report must be updated and submitted within 24 hours to Sponsor (or designee) using the same procedure used for transmitting the initial SAE report.

Sponsor's representative for SAE notifications has the following address:

[contact]

and

Cell Phone: ([contact]

Sponsor will immediately forward SAE notifications (in experimental arm patients) to the following address:

[contact]

or

Facsimile Number: (+1) [contact]

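### The protocol gives conflicting post-treatment safety windows (about 30 days or 100 days), and its SAE window has no defined end for control patients

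*Protocol*

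**What the plan says.** The protocol has two sets of rules for safety data after treatment ends.

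**Chapter 7**
- Section 7.7.3.1 places the safety visit "approximately 30 days after the last dose of trial treatment or before the initiation of a new anti-cancer treatment, whichever comes first" and asks for AE occurring before that visit to be recorded. Ongoing AE above grade 1 are followed to resolution or stabilization, "or until the beginning of a new anti-neoplastic therapy, whichever occurs first".
- Section 7.7.4: "After the end of treatment, each subject will be followed for 30 days for AE monitoring".
- Section 7.3.5: "Once new anti-cancer therapy has been initiated the subject will move into survival follow-up". Section 7.7.3.3 describes that phase as a check of survival status every 6–12 months. The flow chart marks no AE review in it.

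**Flow chart and chapter 8**
- Footnote 6, attached to AE review at the withdrawal, safety and year-1 follow-up visits, requires AE to be "reported for at least 100 days after last dose administration of IMP". It has no arm restriction and no cut-off at new therapy.
- Section 8.1.1 collects non-serious AE to 100 days after the last study drug and says this applies to experimental-arm patients only.
- Section 8.2 covers SAE in both arms, related or not: "All SAE must be collected that occur during the screening period and within 100 days of the last dose of nivolumab". After that, SAE believed related to a study drug or procedure remain reportable for the whole study.

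**Related text**
- Section 5.8.2 collects concomitant medication to 30 days after the last dose. Beyond that: "Concomitant medications administered later than 30 days after the last dose of study treatment should be recorded for SAE".
- Section 5.5 allows experimental patients to have FLOX without nivolumab: "After 24 months, FLOX alone may be administered as per the study dosing schedule in the control arm".
- SAP section 5.5 (Harms) states no collection window. SAP section 5.2 compares safety and tolerability between arms by χ² or Fisher's exact test.

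**The concern.** Immune-related toxicity can appear after the last dose, and a 100-day window would capture it. If some sites stop at 30 days or at the start of the next therapy while others continue to 100 days, late events are ascertained unevenly. Treatment ends by design at progression on therapy (section 5.5), so patients who then start another treatment are an expected group. These are the patients that 7.3.5 and 7.7.3.1 remove from AE follow-up.

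The reference dose adds a second problem. Section 8.2 counts SAE from the last nivolumab dose, although section 5 defines all four drugs as study drugs and control patients never receive nivolumab.

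Safety is a secondary endpoint that is tested between arms. An incidence comparison is hard to interpret if the period over which events are counted differs by site and by arm.

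**Working it through.** The plan states no figure to reproduce here. The check sets the rules side by side and does the day counts.

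**Step 1. The rules**

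| Source | Covers | Ends | Arm | Effect of new therapy |
|---|---|---|---|---|
| 7.7.3.1 | New AE | Safety visit, about day 30 | Not limited | Visit is brought forward |
| 7.7.3.1 | Ongoing AE above grade 1 | Resolution or stabilization | Not limited | Follow-up stops |
| 7.7.4 | AE monitoring | Day 30 after end of treatment | Not limited | Not stated |
| Footnote 6 | AE | At least day 100 after last study drug | Not limited | None stated |
| 8.1.1 | Non-serious AE | Day 100 after last study drug | Experimental only | None stated |
| 8.2 | All SAE | Day 100 after last nivolumab | Both named | None stated |

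The 30-day and 100-day rules cannot both hold. The three 100-day rules also differ from one another in arm and in reference dose.

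**Step 2. Days uncovered for new non-serious AE**
- Under 7.7.4: 100 − 30 = 70 days, or 70% of the window.
- Under 7.7.3.1, if new therapy starts on day d < 30: at least 100 − d days. The documents give no distribution for d. Assuming d = 28 or 14 gives 72 or 86 days.

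**Step 3. Do the year-1 visits fill the gap?** They fall every 3 months ±7 days. Three months is 3 × 365.25/12 = 91.3 days, so the first visit is at about day 84–98 after discontinuation. The second is at 182.6 ± 7, or about day 176–190. If discontinuation coincides with the last dose, no scheduled visit falls between day 98 and day 100, but the second visit can collect events retrospectively. A patient already moved to survival follow-up under 7.3.5 has neither visit.

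**Step 4. The SAE clock when FLOX is the last drug.** Inputs from section 5.5 and the flow chart: cycles every 2 weeks, nivolumab last given at cycle 8 day 1 (week 14), 16 weeks of active therapy, and an 8-week break for the average patient. The next sequence then starts with FLOX at week 16 + 8 = 24.
- Last nivolumab to FLOX cycle 1: (24 − 14) × 7 = 70 days. Window left: 100 − 70 = 30 days.
- Last nivolumab to FLOX cycle 2: 70 + 14 = 84 days. Window left: 100 − 84 = 16 days.

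The break lasts until progression, so other lengths are possible. With an assumed 12-week break the days left are 2 and −12; with 16 weeks, −26 and −40. A negative value means that the window closed before the last study dose.

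**Step 5. Control arm.** The only stated end point in 8.2 is 100 days after nivolumab. With no nivolumab dose, no end date can be calculated.

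**The case against.** A reader might infer that the 100-day window is simply not delivered. The documents do not support that. Footnote 6, 8.1.1 and 8.2 all require it without a new-therapy cut-off, and the flow chart marks AE review at the year-1 visits. What follows is that delivery depends on which section a site applies.

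Other strong readings also fail:

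- **Unresolved toxicity is dropped.** Section 7.7.4 refers AE present at discontinuation to chapter 8, which follows them to resolution or stabilization. Section 7.4 continues laboratory follow-up in the same spirit. The new-therapy stop in 7.7.3.1 is one of several conflicting instructions. It concerns ongoing events and has no 30-day cap.
- **SAE are lost after 30 days.** Section 7.7.3.1 refers to the full study duration, and 8.2 keeps related SAE reportable throughout. Where nivolumab was the last drug, the 8.2 clock is the 100-day window.
- **FLOX alone leaves a long period without SAE data.** The route needs 24 months (about 104 weeks) of active therapy. That is 6.5 sequences of 16 weeks with six 8-week breaks: 104 + 48 = 152 weeks, or about 35 calendar months, against 30 months of expected follow-up. AE are also reviewed at every treatment visit. FLOX continuing after nivolumab is stopped for toxicity is not stated in 5.5 or 5.7.2.3.
- **Steroids for late events go unrecorded.** Section 5.8.2 also asks for corticosteroid details during the study. The 30-day limit bears more on other medication.

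It is also fair to say that SAP section 5.5 records only grade 3–5 events and grade 2 immune-related hepatotoxicity. Many late low-grade events would therefore not enter the analysis under any window.

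These points narrow the concern. They do not remove the contradiction, the undefined control-arm window or the SAE clock tied to one drug.

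**Conclusion.** The protocol contradicts itself on post-treatment safety collection, and the SAP does not resolve it. Applied literally, 7.7.4 leaves up to 70 of the 100 days uncovered for new non-serious AE. The figure is larger under 7.7.3.1 only if new therapy starts before day 30, and the documents do not say how often that happens. For SAE regardless of cause, the 8.2 window is undefined in the control arm. It is cut to 30 or 16 days for an experimental patient who stops after FLOX cycle 1 or 2 of a new sequence, given the protocol's 8-week break.

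The size of any bias in the safety comparison cannot be calculated, because it depends on site practice and on the timing of new therapy. The text should be corrected, since following one section literally yields incomplete late-toxicity data and the correction costs little.

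**What to change.** **Protocol.** Reconcile 7.3.5, 7.7.3.1, 7.7.4 and 8.2 with footnote 6 and 8.1.1. State one AE/SAE collection window for each arm, including the control arm, timed from the last dose of any study drug. State that starting new anti-cancer therapy does not close collection, and record its start date so that events can be shown before and after it. Bring the 30-day limit on concomitant medication in 5.8.2 into line with that window.

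**SAP.** In sections 5.2 and 5.5, name one common post-treatment window for the between-arm safety comparison, so that ascertainment is equal. If one arm's collection window is longer, report the extra events descriptively. This equalises only the post-treatment period. The difference in expected time on treatment (18 against 9 months) is a separate matter.

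**Cost.** A protocol clarification, a short SAP addition, and one phone or record check near the end of the window for patients already on new therapy. Some late events will be confounded by that therapy; the recorded start date makes this visible.
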